#### 10. Risks and Benefits

#### 10.1. Potential Risks

There are no known incremental risks associated with participating in this study.

### 10.2. Risks Outlined in the Instructions for Use (IFU)

Refer to the appropriate Instructions for Use (IFU) for the OsteoCool™ RF Ablation system components for updated list on contraindications, precautions, warnings, adverse events, directions for use and other product specific details.

#### **10.2.1.** OsteoCool™ RF Ablation Probe Kit

### Indications for Use (US):

The OsteoCool™ RF Ablation Probe Kit, in combination with other components of the OsteoCool™ RF Ablation System, is intended for:

- Palliative treatment in spinal procedures by ablation of metastatic malignant lesions in a vertebral body.
- Coagulation and ablation of tissue in bone during surgical procedures including palliation of pain associated with metastatic lesions involving bone in patients who have failed or are not candidates for standard therapy.
- Ablation of benign bone tumors such as osteoid osteoma.

#### Indications for EUR and CAN:

[figure not shown]
The OsteoCool™ RF Ablation Probe Kit, in combination with other components of the OsteoCool™ RF Ablation System, is intended for ablation of benign bone tumors such as osteoid osteoma and palliative treatment by ablation of metastatic malignant lesions involving bone, including the vertebral body.

#### **Contraindications**:

- Use of the OsteoCool™ RF Ablation System is contraindicated in patients with heart pacemakers or other electronic device implants. (Europe and Canada only)
- Use of the OsteoCool™ RF Ablation System device is contraindicated in vertebral body levels C1-C7.

#### Warnings:

- Do not use in patients who have electronic implants such as cardiac pacemakers without first consulting a qualified professional (e.g., cardiologist). A possible hazard exists because interference with the action of the electronic implant may occur, or the implant may be damaged. (US only)
- The OsteoCool™ RF Ablation Probe Kit contains single use devices. They should not be re-sterilized
  or re-used. Reuse can cause the patient injury and/or the communication of infectious disease(s)
  from one patient to another.
- Take appropriate precautions for patients with blood coagulation disorders, anticoagulant use, neurological deficit, or systemic infection or local infection in area of the procedure.

- The procedure is to be performed with minimal to moderate sedation to allow the patient to remain in a communicative state for patient feedback.
- Adequate measures must be taken to minimize x-ray exposure while using fluoroscopy. This exposure can result in acute radiation injury as well as increased risk for somatic and genetic effects.
- Do not modify the equipment as this may compromise safety and efficacy.
- When the OsteoCool™ RF Generator is activated, electrical fields may interfere with other electrical medical equipment.
- During power delivery, the patient should not be allowed to come in contact with grounded metal surfaces.
- Discontinue use if inaccurate, erratic, or sluggish temperature readings are observed. Use of damaged equipment may cause patient injury.
- For safe use of the OsteoCool™ RF Ablation System, the physician should have specific training, experience, and through familiarity with the use and application of this product.
- Do not ablate in painful osteoporotic vertebra without tumor.
- Do not use the device in fractures due to prostatic cancer or other osteoblastic metastases to the spine.
- Do not use the products in dense (sclerotic) bone including traumatic high energy fracture as device damage resulting in patient injury may occur.
- [US only]Do not use this device in patients without metastatic malignant lesions in bone or in the vertebral body.
- [EU and CAN only) Do not use this device in patients without osteoid osteoma or metastatic malignant lesions in bone or in the vertebral body.
- When using this device in the vertebral body, do not use this device in patients with multiple myeloma, solitary plasmacytoma, or primary malignant lesions in the index vertebra.
- Do not use this device in more than one vertebral body.
- Do not touch the electrode tip while power is being applied.
- Do not withdraw the OsteoCool™ RF Ablation Probe while power is being applied to ablate lesions.
- Use standard electrosurgical cautions when using the OsteoCool™ RF Ablation System in the vicinity of nerves and nerve roots.
- Ablation must be performed under fluoroscopic guidance. Do not perform ablation without imaging as it will result in severe injury to the patient.
- When using this device in the vertebral body, the OsteoCool™ RF Ablation Probe must be positioned
  within the vertebral body such that when ablation is performed per the thermal distribution graphs,
  nerves and nerve roots are beyond the ablation zone. Failure to follow the thermal distribution
  graphs will result in severe injury to the patient.
- Precautions during ablation near organ surface or near vasculature Due to the non-homogenous
  conduction and convection of heat in this anatomy, shapes of ablations performed on tissue that is
  near the organ surface or near vasculature may not be spherical. Careful planning should be done
  for targets that require ablation in these locations.
- Any application or procedure that alters tissue perfusion and affects temperature elevation should be monitored carefully.

- High power settings can cause local desiccation of tissue, which can impede the ability to produce expected ablations. Set power as low as possible for intended purpose. Follow manufacturer's guidelines of time at temperature for ablation generation. If the recommended times and temperatures are not achieved there can be no assurance that the desired ablation volume has been created. Standard techniques for evaluation (e.g. CT or MRI) should be used to determine the actual extent of all ablations.
- It is important to carefully evaluate all candidates for this procedure for evidence of impending fracture, particularly in weight-bearing bone. Do not perform RF ablation of metastases in weight-bearing bone with evidence of impending fracture. Note: Pathologic fracture is more prevalent and serious in long bone.
- It is important to carefully evaluate all candidates for this procedure for proximity of the metastasis
  to critical structures. Ensure that device placement is at least 1cm away from the structures not
  intended for ablation. Proximity to nerve structures is particularly critical. Serious complications
  such as incontinence can occur if these critical structures are damaged during the RF ablation
  procedure.
- The durability of pain relief after using this device to ablate painful bone metastases has not been established.

#### **Precautions**:

- The OsteoCool™ Tube Kit should never be disconnected from the OsteoCool™ RF Ablation Probe when RF delivery is in progress. The lumen of the tube kit should not be obstructed in any way during the procedure, as this will stop cooling of the probe.
- Disconnect the OsteoCool™ RF Ablation Probe by pulling the connector, not the cable.
- Handle the OsteoCool™ RF Ablation Probe safely when it is in use due to electric currents and the hot tip.
- Do not bend the OsteoCool™ RF Ablation Probe as this may damage the insulation.
- Do not remove or withdraw the OsteoCool™ RF Ablation Probe while energy is being delivered to ablate lesions.
- While inserting the OsteoCool™ RF Ablation Probe through the Introducer watch the fluoroscope for any buckling. Do not attempt to further insert the probe if any buckling is observed or significant resistance is felt.
- Do not move the Introducer when the OsteoCool™ RF Ablation Probe is in it. If repositioning is needed, retract the probe from the introducer and then reposition the introducer with the stylet inserted.
- The physician must determine, assess, and communicate to each individual patient all foreseeable risks of the RF procedure.
- The "Temperature" displayed on the generator while in "Ablate" refers to the cooled electrode temperature and not the hottest tissue temperature.

#### **Adverse Events**:

#MDT16075 Version 4.0 Page 45 of 81

The OsteoCool™ RF Ablation Probe Kit is used with other components of the OsteoCool™ RF Ablation System in RF lesion procedures. Adverse events associated with the use of this device are similar to those indicated for medicated and anesthetic methods utilized in other surgical procedures.

- As a consequence of electrosurgery, damage to surrounding tissue through iatrogenic injury could occur.
- Nerve injury including thermal injury, puncture of the spinal cord or nerve roots potentially results in radiculopathy, paresis, and paralysis.
- Pulmonary embolism
- Hemothorax or pneumothorax
- Infection including deep or superficial wound infection
- Unintended puncture wound including vascular puncture and dural tear
- Hemorrhage
- Hematoma
- Pain

### **10.2.2.** OsteoCool Bone Access Kit

#### Warnings:

Breakage of the device may require intervention or retrieval.

#### **Precautions:**

The OsteoCool™ Bone Access Kit is a single use device intended to contact body tissues. Do not reuse, reprocess, or resterilize. Reusing these devices carries the risk of contamination and may cause patient infection or cross-infection, regardless of the cleaning and resterilization methods. There is also an increased risk of the deterioration of the devices performance due to the reprocessing steps, which may lead to patient injury or death.

- It is important to read the Instructions for Use and these precautions carefully prior to device operation.
- Use the devices prior to the use by date noted on the package.
- Do not use if package is opened or damaged because product integrity including sterility may be compromised.
- Do not use damaged products. Before use, inspect all system components and packaging to verify no damage has occurred.
- Do not use this product if you have not been properly trained in its use. Physicians using the devices should be familiar with the physiology and pathology of the selected anatomy, and be trained in the performance of the chosen surgical technique.
- Components of each system should be manipulated only while under fluoroscopic observation with radiographic equipment that provides high quality images.
- Access to the vertebral body via the pedicle requires a minimum pedicle width of 5mm. Insertion of
  the instruments requires specific knowledge of the dimensions of the site of insertion to bone as
  assessed by MRI, CT, or other imaging method.
- Never use electric or other powered instruments/devices in conjunction with the OsteoCool™ Bone Access Kit. Use only manual power when using the OsteoCool™ Bone Access Kit.

#MDT16075 Version 4.0 Page 46 of 81

Do not resterilize and/or reuse. The OsteoCool™ Bone Access Kit is for single use only.
 Reconditioning, refurbishing, repair, modification, or resterilization of the device to enable further use is expressly prohibited.

PHYSICIAN NOTE: Although the physician is the learned intermediary between the company and the patient, the important medical information given in this document should be conveyed to the patient.

#### **Adverse Events:**

Adverse events potentially associated with use of the device include:

- Nerve injury including puncture of the spinal cord or nerve roots potentially resulting in radiculopathy, paresis, or paralysis
- Embolism of fat, thrombus, or other materials resulting in symptomatic pulmonary embolism or other clinical sequelae
- Hemothorax or pneumothorax
- Deep or superficial wound infection
- Unintended puncture wounds including vascular puncture and dural tear
- Bleeding or hemorrhage
- Hematoma
- Pain

# 10.3. Risk of Imaging/Radiation

Subjects will be exposed to a small amount of radiation that they will receive during the study. The amount of this radiation cannot be determined in advance. For example, during the initial procedure, fluoroscopy or CT may be used according to standard of care at the site or an Investigator may order pre-operative or post-operative x-ray films or CT scans to assess the lesions/tumors. These images are routine and according to the standard of care; therefore no additional radiation risk is associated with participation in this clinical study.

#### 10.4. Potential Benefits

An analysis of radiofrequency tumor ablation literature concluded that, the use of ablation techniques, particularly radiofrequency energy-based methodologies, have proven to be effective in providing significant pain relief in the majority of subjects, with minimal failures or complications reported. 38, 23, 39

There may be no direct benefits of study participation. However, subject participants will undergo an enhanced level of clinical scrutiny compared to routine clinical care, which may provide some indirect health benefits. Participation contributes to expand the knowledge base with respect to the treatment of bone metastasis in the spine.

#MDT16075 Version 4.0

Page 47 of 81

Medtronic

#### 10.5. Risk-Benefit Rationale

Participation in this study will not expose the subject to greater risks than if he/she were receiving OsteoCool RF Ablation system outside of the study. There might be other discomforts and risks related to OsteoCool RF Ablation system and/or this study that are not foreseen at this time.

The risks associated with OsteoCool RF Ablation system are minimized in this study by selecting only qualified Investigators experienced in RF ablation procedures of the vertebral body and/or bone, selecting an appropriate patient population via inclusion/exclusion screening, and monitoring subject functional progress and events reported for this study. The review and minimization of the potential risks to the patient and the potential benefits to the patient support the conduct of this study.

### 11. Adverse Events and Device Deficiencies

### 11.1. Definitions/Classifications

Any adverse event meeting the definition of: device, therapy, and/or procedure related as well as all device deficiencies will be considered reportable for this study. Medtronic will classify each adverse event according to ISO 14155:2011. Adverse events and device deficiencies are defined as follows:

#MDT16075 Version 4.0 Page 48 of 81

### **Table 11-1: Definitions**

Term	General
Adverse Event (AE) (ISO14155:2011 3.2)	Any untoward medical occurrence, unintended disease or injury, or untoward clinical signs (including abnormal laboratory findings) in subjects, users or other persons, whether or not related to the investigational medical device.  Note 1: This definition includes events related to the investigational medical device or the comparator.  Note 2: This definition includes events related to the procedures involved.  Note 3: For users or other persons, this definition is restricted to events related to investigational medical devices.
Adverse Device Effect (ADE) (ISO14155:2011 3.1)	Adverse event related to the use of an investigational medical device.  Note: This definition includes adverse events resulting from insufficient or inadequate instructions for use, deployment, implantation, installation, or operation, or any malfunction of the investigational medical device.  Note: This definition includes any event resulting from use error or from intentional misuse of the investigational medical device.
Device Deficiency (DD) (ISO 14155:2011 3.15; ISO 14155:2011 3.27; ISO 14155:2011 3.43;)	Inadequacy of a medical device with respect to its identity, quality, durability, reliability, safety or performance.  Note: Device deficiencies include malfunctions, use errors, and inadequate labeling.  Malfunctions: Failure of an investigational medical device to perform in accordance with its intended purpose when used in accordance with the instructions for use or Clinical Investigational Plan (CIP)  Use Error: Act or omission of an act that results in a different medical device response than intended by the manufacturer or expected by the user  Note 1: Use error includes slips, lapses, and mistakes.  Note2: An unexpected physiological response of the subject does not in itself constitute a use error.

#MDT16075 Version 4.0 Page 49 of 81

SERIOUSNESS			
Serious Adverse	An adverse event that		
Event (SAE)	a) led to death,		
(ISO 14155:2011	b) led to serious deterioration in the health of the subject, that either		
3.37)	resulted in:		
	1. a life-threatening illness or injury, or		
	2. a permanent impairment of a body structure or a body function, or		
	3. in-patient or prolonged hospitalization, or		
	4. medical or surgical intervention to prevent life-threatening illness or		
	injury or permanent impairment to a body structure or a body		
	function,		
	c) led to foetal distress, foetal death or a congenital abnormality or birth		
	defect.		
	Note: Planned hospitalization for a pre-existing condition, or a procedure required		
	by the CIP, without serious deterioration in health, is not considered a serious		
	adverse event.		
Serious Adverse	Adverse device effect that has resulted in any of the consequences characteristic		
Device Effect	of a serious adverse event		
(SADE)			
(ISO 14155:2011			
3.36)	Cariaus adversa davias affect which by its natura, incidence, soverity or outcome		
Unanticipated Serious Adverse	Serious adverse device effect which by its nature, incidence, severity or outcome		
Device Effect	has not been identified in the current version of the risk analysis report		
(USADE)	Note 1: Anticipated serious adverse device effect (ASADE) is an effect which by its		
(ISO 14155:2011	nature, incidence, severity or outcome has been identified in the risk analysis		
3.42)	report.		
RELATEDNESS			
Relationship of	The relationship of the adverse event to the study treatment (device, therapy		
Adverse Events	and/or procedure) will be described by the investigator using the following terms:		
	Not related		
	• Unlikely		
	• Possible		
	
 
Probable
 
		
	Causal relationship		

#MDT16075 Version 4.0 Page 50 of 81

Severity	
Severity of the	The investigator's assessment of severity must be provided for AEs reported for
Adverse Events	this study. The following classifications are to be used to classify the severity of
	the reported safety event:
	Mild: The AE is noticeable to the patient but does not interfere with routine
	activity.
	Moderate : The AE interferes with routine activity but responds to symptomatic
	therapy or rest.
	Severe: The AE significantly limits the patient's ability to perform routine
	activities despite symptomatic therapy. All hospital admissions or emergency
	room (ER) visits are graded at least as severe.
SIR AE Classification	on .
Society of	Minor Complications
Interventional	A. No therapy, no consequence
Radiology (SIR)	B. Nominal therapy, no consequence; includes overnight admission for
Classification	observation only.
System for	Major Complications
Complications by	C. Require therapy, minor hospitalization (<48 hours)
Outcome	D. Require major therapy, unplanned increase in level of care, prolonged
	hospitalization (>48 hours)
	E. Permanent adverse sequelae
	F. Death.

For the OPuS One clinical study, cement extravasations are reportable if:

- 1. The extravasation is >15 mm; or
- 2. If the extravasation of any volume of cement results in any adverse event (e.g., spinal cord compression, nerve injury, embolic event).

Extravasation that does not result in a negative clinical event will not be considered as an adverse event for this study.

### 11.2. Reporting of Adverse Events

Any adverse event meeting the definition of device, therapy and/or procedure related as well as all device deficiencies that occur from enrollment through subject discontinuation from the study will be collected.

The following categories of adverse events will be collected for this study from enrollment to the end of the study:

- All device, therapy and/or procedure-related adverse events including events related to:
  - The device components and/or procedure (Bone Access Kit, Probe, generator, etc.)
  - o Surgery or anesthesia regarding the initial or repeat procedure

#MDT16075 Page 51 of 81 Version 4.0

In addition, all device deficiencies reported during the study will be collected. Worsening of pain symptoms at the treated site will be collected as part of the efficacy measures and are not considered a reportable adverse event unless the nature, severity, duration and or frequency of pain at that location has changed. All reportable adverse events will be classified using the following responsibility matrix:

**Table 11-2: Event Classification Responsibilities** 

What is Classified	Who Classifies	Classification Parameters
Relatedness	Investigator	Procedure related
	CEC (deaths only)	Device/therapy related
USADE potential	Medtronic	USADE
SIR Classification	Medtronic	SIR AE Classification
Seriousness	Investigator	SAE/SADE
Diagnosis	Investigator	Based on presenting signs and symptoms and other supporting data
	Medtronic	MedDRA term assigned based on the data provided by investigator

All reportable events must be recorded in the subject's medical record and on the Adverse Event and/or Device Deficiency eCRF and promptly reported to Medtronic. IRB/EC reporting must be completed in accordance with the policies of the governing IRB/EC. Competent Authority reporting should be in accordance with applicable local regulations.

It is the responsibility of the Investigator to identify the occurrence of reportable adverse events and device deficiencies and to ensure the required information is accurately documented on the eCRF. Reports of adverse events and device deficiencies will include the following information, at a minimum:

- Date of event
- Diagnosis or description of the event
- Assessment of the seriousness and relationship to the product(s) under study
- Treatment
- Outcome and date of resolution

The clinical course of each adverse event must be followed until resolution or subject discontinuation from the study, whichever comes first. "Ongoing" adverse events and device deficiencies must be assessed at each protocol required visit, and new or updated information must be documented on the Adverse Event and/or Device Deficiency eCRF and promptly reported to Medtronic and if applicable to the IRB/EC.

If necessary, the Investigator may report to the sponsor initially by telephone or email and follow-up with completed eCRFs and, if possible, copies of source documentation regarding the event (e.g., physician/nurse notes or summaries).

Medtronic study personnel will promptly review all reported adverse events and device deficiencies and if necessary request clarification and/or additional information from the Investigator. If Medtronic disagrees with the Investigator's assessment of the adverse event relationship to the device and/or procedure, Medtronic study personnel will document the disagreement and report or ensure reporting

of both opinions to the IRB/EC as necessary. All reported adverse events and device deficiencies will be reviewed by a Medtronic Medical Advisor to ensure consistent reporting.

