Patients experienced a mean pain score of 5.9 on a 0–10 scale at baseline. Pain decreased to a mean of 3.7 immediately after the procedure with additional reduction to 2.1 at month 3. On a patient-by patient basis, pain relief was rapid with 32/49 (65%) of the patients experiencing ≥2 point change within 3 hours of treatment. Pain Scores decrease was statistically significant at each follow-up time point. Of the patients who received RFA without cement augmentation, all patients (3/3) demonstrated clinical success immediately after the procedure with a mean improvement of 4.3 NPRS points. At the last follow-up visit for all non-cemented patients, mean improvement was 5.0 NPRS points.

Page 18 of 81

Medtronic

The modified ODI improved from 52.9 at baseline to 37.0 (p<0.08) at the 3 month visit. The FACT-G7 improved from 10.9 to 16.2 (p = 0.0001) and the FACT-BP improved from 22.6 to 38.9 (p<0.001).

There were six adverse events reported in six patients during the course of this study. This included: pain outside the target vertebrae due to progression of the primary or other metastatic disease (n=3), ruptured disk (n=1) adjacent to the index vertebra, neuropathic pain (n=1) and syncope (n=1). The ruptured disk was present prior to treatment of the index vertebrae, became painful (between the month 1 and month 3 visit) and was resolved following bilateral nerve blocks. Neuropathic pain was present prior to the procedure and intermittent after the procedure (n=1). The operating physicians deemed five of the adverse events as unrelated and one, the ruptured disk, as unlikely related to the RFA and/or vertebral augmentation procedures.

The authors concluded that radiofrequency ablation with or without vertebral augmentation was a safe, effective and durable treatment for patients with painful metastatic vertebral body tumors.

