### **Data Collection and Endpoint Definitions**

Reported adverse events and device deficiencies will be collected on eCRFs. They will be coded and summarized using the most recent Medical Dictionary for Regulatory Affairs (MedDRA).

Adverse event relationships will be collected for the study procedure, study therapy, OsteoCool system, and any other device. Relationship strength is categorized as (in order) Not Related, Unlikely, Possible, Probable, or Causal. Adverse events will be considered as "related" if any of the Possible, Probable, or Causal categories are indicated. Deaths will be collected on the Study Exit form and the Adverse Event form if applicable. The study will utilize an independent Clinical Events Committee (CEC) to adjudicate deaths to determine the relationship of the death to the device, procedure and/or therapy.

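### A non-fatal event gets a required adverse-event record only if the investigator judges it related, and no stated check reaches a wrong 'not related' call

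*Combined protocol and SAP*

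**What the plan says.** CIP 11.2 sets the scope of collection: "Any adverse event meeting the definition of device, therapy and/or procedure related as well as all device deficiencies that occur from enrollment" until the subject leaves the study. CIP 11.1 has the same limit. The investigator applies the test: "It is the responsibility of the Investigator to identify the occurrence of reportable adverse events and device deficiencies". Table 11-2 also gives the relatedness judgement to the investigator and adds the CEC for deaths only.

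Two sponsor checks follow in 11.2. First, "If Medtronic disagrees with the Investigator's assessment of the adverse event relationship to the device and/or procedure, Medtronic study personnel will document the disagreement", and both opinions then go to the IRB or EC as necessary. Second, "All reported adverse events and device deficiencies will be reviewed by a Medtronic Medical Advisor to ensure consistent reporting".

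Deaths are handled differently. Under 11.6 every death is reported to the sponsor whatever its cause, and under section 12 the CEC adjudicates its relationship to treatment.

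SAP 7.10 repeats that only related events were reportable, and uses this to leave untreated subjects out of the safety analysis. It grades relationship on five levels and counts an event as related "if any of the Possible, Probable, or Causal categories are indicated".

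**The concern.** There is no comparator arm, so the incidence of related events is the main safety result. Both documents also give richer safety reporting as a reason for enrolling 250 subjects rather than about 52. Yet the judgement that defines the result also decides whether an event enters the database, and it is made at the treating site by someone who knows what was done.

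In metastatic disease, tumour progression is a ready alternative explanation for several harms the protocol itself names. CIP 10.2.1 and 10.2.2 list nerve injury with radiculopathy, paresis or paralysis, infection, haemorrhage and haematoma; the warnings in 10.2.1 add fracture. If such an event is put down to the tumour when the procedure caused it, 11.2 asks for no adverse-event form. It may then be unrecoverable at analysis.

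**Working it through.** The plan states no figure on this point. The check is mainly a comparison of the reporting steps.

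**1. Which check can reach which event?**

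| Step | Source | Events reached |
|---|---|---|
| Entry to the database | CIP 11.1, 11.2 | Those the investigator judges related |
| Sponsor review of relatedness | CIP 11.2 | Reported events |
| Medical Advisor review | CIP 11.2 | Reported events |
| CEC adjudication | CIP 12, Table 11-2 | Deaths |
| Safety tables | SAP 7.10 | Reported events |

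A non-fatal event judged unrelated and not reported appears in no row below the first. Leaving it out complies with 11.2, so source data verification (15.1), which supports the data on the eCRFs, would not necessarily flag it.

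**2. Does other text close the gap?**

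- *Serious events.* Table 14-1 asks for all SAEs without a relatedness condition, and CIP 13.5.2 presents unrelated SAEs separately. CIP 11.1, 11.2 and SAP 7.10 restrict reporting to related events, and SAP 7.10 has no table of unrelated SAEs. The documents conflict.
- *Non-serious events.* Table 14-1 has a row for all other adverse events, again with no relatedness condition. It does not say that it widens 11.2, CIP 14.2 asks only for related events, and the SAP reads the rule as related-only.
- *Indirect traces.* The BPI records pain. The 15 mm rule in 11.1 concerns cement. Follow-up images are collected only if available, in the US and Canada, and the tumour-control assessment is optional. None of these is an adverse-event record of paresis, infection or haematoma.

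**3. What do the cited series show?** (CIP 4.4)

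- Fifty-patient spine series: six events in six patients, 6/50 = 12% (Clopper-Pearson 95% CI 4.5% to 24.3%). "The operating physicians deemed five of the adverse events as unrelated and one, the ruptured disk, as unlikely related". At this study's cut of Possible or higher, 0 of the 6 would be classed as related. Three were pain outside the target vertebrae and one was syncope. The other two, the ruptured disk and the neuropathic pain, were present before treatment.
- Posterior vertebral body series: transient radicular symptoms after ablation in 4/26 = 15.4%.

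Neither series measures misattribution.

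**4. Illustration under assumed rates.** Let n = 100 (the enrolment goal for vertebral-only subjects), p = the true proportion of subjects with a related event, and m = the share of those events wrongly attributed to the tumour. Both p and m are assumptions. Subjects are taken as independent, with at most one event each and no errors in the other direction. The expected number of subjects with a recorded event is n × p × (1 − m).

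| p | m = 0 | m = 0.25 | m = 0.50 |
|---|---|---|---|
| 2% | 2.0 | 1.5 | 1.0 |
| 5% | 5.0 | 3.75 | 2.5 |
| 10% | 10.0 | 7.5 | 5.0 |

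The chance of recording none is [1 − p(1 − m)]^n. At p = 2% it is 0.98^100 = 0.13 with m = 0, 0.985^100 = 0.22 with m = 0.25, and 0.99^100 = 0.37 with m = 0.50.

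**The case against.** The strongest reply is that the plan does what it sets out to do. The safety measure is the incidence of related events, in a post-market study within the approved indication and with no safety hypothesis. Without a comparator, an all-cause count of local events in progressing disease cannot isolate device harm. The cut at Possible also admits doubtful events that the tumour caused, so the net direction of error is not fixed. Additional Measures and CIP 9.6.8 are blank in the public copy, so what else records local outcomes cannot be fully judged. All of this stands, but it does not supply a check on an event that was never reported.

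Three stronger readings are tempting, and the documents support none of them.

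- *Sponsor review can only remove events.* No text lets the sponsor delete or downgrade an event; a disagreement is documented and both opinions are passed on. SAP 7.10 records relationship separately for procedure, therapy, OsteoCool system and any other device, so an event filed as procedure-related but Unlikely for the device could be disputed upward.
- *Events blamed on the tumour leave no record at all.* Table 14-1 and CIP 13.5.2 point to unrelated SAEs being reported, and several of the harms at issue would be serious if they led to hospitalisation or permanent impairment. What is missing is a required adverse-event record.
- *The fifty-patient series shows harms this rule would lose.* Its two local or neurological events pre-dated treatment, so calling them unrelated or unlikely related may well have been correct.

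**Conclusion.** The point holds in limited form. For non-fatal events, the investigator's relatedness judgement is the entry condition under CIP 11.1, 11.2 and SAP 7.10, and no stated check reaches a wrong 'not related' call on an event left unreported. The case is clearest for non-serious events at or next to a treated site. For serious events it depends on how the conflict between CIP 11.1, 11.2 and SAP 7.10 on one side and Table 14-1 and CIP 13.5.2 on the other is resolved; resolving it would still leave the non-serious events uncovered.

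A related event wrongly put down to the tumour lowers the reported incidence. How often this would happen is unknown, and the 2% to 10% rates and 25% to 50% shares above are assumptions. The point does not touch the primary pain analysis. It deserves a change because the remedy is cheap and the plan already accepts the principle for deaths.

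**What to change.** **CIP 11.2.** Add a short list of new or worsened events at or next to a treated site that are reportable whatever the attribution, drawn from the protocol's own warnings and adverse-event lists in 10.2.1 and 10.2.2: nerve injury, radiculopathy, paresis or paralysis; fracture; infection; haemorrhage or haematoma. Record the existing five-grade relatedness for each.

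**SAP 7.10.** Show the incidence of all listed events beside the incidence of those judged related, so a reader can see how much rests on attribution.

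**Both documents.** Reconcile CIP 11.1, 11.2 and SAP 7.10 with Table 14-1 and CIP 13.5.2 on whether unrelated SAEs are collected and tabulated.

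**Cost.** CIP and SAP wording, and additional Adverse Event eCRFs, some of which will turn out to describe disease progression. No extra visits, procedures or assessors. The displayed event rate will look less favourable, and the text should say that the all-cause column is not an estimate of device harm. Subjects whose follow-up ended before the change would not be covered, and the reports should say so.
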